1 RESEARCH REFERENCE NUMBERS

Sponsor Protocol Number:	PID16777
Clinical Trials Unit (CTU)	OCTRU376
Reference:	
Funder Reference:	NIHR134344
Ethics Reference Number:	23/NW/0104
IRAS Number:	319230
Registry:	ISRCTN: 14417629

5 LAY SUMMARY/PLAIN ENGLISH SUMMARY

There are over 15,800 new cases of gullet (oesophageal) or stomach cancer diagnosed every year in the UK, with over 12,300 deaths per year attributed to these cancers. Currently, most patients with cancer of the gullet and stomach are treated with surgery with or without additional chemo- or radio-therapy. In recent years there have been improvements in survival from these two cancers, due to better therapies, less invasive surgery and earlier detection. Despite these improvements, in around two-thirds of patients treated with surgery, the cancer will return and lead to death within three years.

At present there is very little evidence as to how gullet and stomach cancer patients should be followed up after surgery and whether different methods of follow-up could improve survival. Currently, national and international guidelines do not provide consistency in their recommendations for follow-up after surgery.

The SARONG study will investigate if regular radiological scans can lead to earlier detection of a cancer returning, at a stage when it may be more readily treatable. This means that participants who agree to take part will be allocated by chance to either more intensive surveillance (including regular radiological scans and a camera test (endoscopy)) or the current standard of care. The study aims to recruit at least 952 participants in the UK over a 32-month period from at least 24 NHS hospitals. Patients undergoing surgery for gullet or stomach cancer will be invited to participate in the study up to 12 weeks after this surgery.

(i) The intensive surveillance group will receive a review in clinic or by telephone with a member of the surgical team, and a radiological scan at 6, 12, 18, 24, 30 and 36 months after randomisation. They will also receive endoscopy at 12 months after randomisation.

(ii) The standard care group will receive a review in clinic or by telephone at 6 and 12 months. After this they will be either discharged to their local doctor or receive a review in clinic with a member of the surgical team every year.

The main aim of this study will be to determine whether earlier detection of cancer through more intensive follow-up results in improved survival and better quality of life for patients with gullet or stomach cancer.

Consultation with patient groups and charities, including Heartburn Cancer UK, Oesophageal and Stomach Cancer Patient Support group, Action against Heartburn, and GUTS charity UK, has taken place and patients will continue to be integral to the organisation and running of the study. The findings will be presented at national and international meetings, published in a high-impact scientific journal and disseminated with a broader social media strategy. All participants taking part in the study will be informed of the findings via the study website. We anticipate the results of the study may have significant practice-changing impact for patients undergoing follow-up after surgery for gullet and stomach cancer.

6 STUDY SYNOPSIS

Full Study Title:	Open label randomised controlled trial of intensive surveillance vs. standard postoperative follow-up in patients undergoing surgical resection for oesophageal and gastric cancer	
Short Title:	Surveillance After Resection of Oesophageal aNd Gastric cancer (SARONG) trial	
Study Acronym:	SARONG	
Study Design:	SARONG is a multicentre, parallel g superiority randomised controlled	roup, two-arm, open-label trial (RCT)
Study Participants/Target Population:	The SARONG study will recruit adul surgical resection for curatively inte gastric cancer with or without neoa chemo(radio)therapy	ts (aged 16 years or over) receiving ended treatment of oesophageal or adjuvant/adjuvant
Eligibility criteria:	 Inclusion: Patients who have undergone surgical resection for curatively intended treatment of oesophageal or gastric cancer (adenocarcinoma and squamous cell carcinoma) with or without neoadjuvant/adjuvant chemo(radio)therapy or immunotherapy (or in combination) Aged 16 years or over Patients willing and able to give informed consent Exclusion: Patients with other cancers undergoing treatment or surveillance for this cancer 	
No. of study arms	2	
Intervention	Intensive surveillance (including rad and pelvis) and clinical review) even randomisation along with an endos randomisation.	diological scans (chest, abdomen ry 6 months for 36 months post- scopy at 12 months post-
Comparator	Standard of care follow-up for 36 m at 6 and 12 months post-randomisa	nonths, comprising clinical review ation.
Planned sample size:	952 participants (476 per trial arm)	
Target no. of centres:	At least 24 NHS Hospitals in the UK	
Follow-up duration:	Each participant will be followed-up randomisation	p for 36 months from
	Objective	Outcome Measure
Primary objective and outcome measure	To assess whether intensive surveillance, including regular radiological investigations and an endoscopic investigation after completing curatively intended treatment, improves survival in patients with oesophageal or gastric cancer.	All-cause mortality at 3 years post-randomisation, defined as death from any cause. Participants who have not been observed to die during the course of the study will have their survival time censored at their last known follow-up date.

Refer to the OBJECTIVES AND OUTCOME MEASURES section of the main protocol for full study objectives and outcome measures.

7 ABBREVIATIONS

AE	Adverse Event
AR	Adverse Reaction
AUGIS	Association of Upper Gastrointestinal Surgeons for Great Britain and Ireland
CA	Cancer Antigen
CEA	Carcinoembryonic Antigen
CI	Chief Investigator
CI	Confidence Interval
CONSORT	Consolidated Standards of Reporting Trials guideline
CRF	Case Report Form
СТ	Computerized Tomography
ctDNA	circulating tumour DNA
CTU	Clinical Trial Unit
CWS	Cancer Worry Scale
DMC	Data Monitoring Committee
DSMC	Data & Safety Monitoring Committee
ENSURE	European multi-centre cohort study
ESMO	European Society for Medical Oncology
GCP	Good Clinical Practice
GDPR	General Data Protection Regulation
GP	General Practitioner
HEAP	health economics analysis plan
HQIP	Healthcare Quality Improvement Partnership
HRA	Health Research Authority
HRQoL	Health-Related Quality of Life
ICER	Incremental Cost Effectiveness Ratio
ICF	Informed Consent Form
IDMC	Independent Data Monitoring Committee
ISDE	International Society for Diseases of the Esophagus
ISRCTN	International Standard Randomised Controlled Trials Number
MedDRA	Medical Dictionary for Regulatory Activities
MHRA	Medicines and Healthcare products Regulatory Agency
NCAPOP	National Clinical Audit and Patient Outcomes Programme
NCCN	National Comprehensive Cancer Network
NCIMI	National Consortium for Intelligent Medical Imaging
NCRAS	National Cancer Registration and Analysis Service
NCRI	National Cancer Research Institute
NHS	National Health Service
NOGCA	National Oesophago-Gastric Cancer Audit

NRES	National Research Ethics Service
OCTRU	Oxford Clinical Trials Research Unit
ONS	Office of National Statistics
00S0	Oxfordshire Oesophageal and Stomach Organisation
OPA	Oesophageal Patient Association
OR	Overall Response
OUH	Oxford University Hospitals NHS Trust
PET-CT	Positron Emission Tomography-CT
PI	Principal Investigator
PICs	Participant Identification Centres
PIS	Patient Information Sheet
PPI	Public and Patient Involvement
QA	Quality Assurance
QALY	Quality Adjusted Life Year
QC	Quality Control
RCT	Randomised Clinical Trial
REC	Research Ethics Committee
SAE	Serious Adverse Event
SAP	Statistical Analysis Plan
SDV	Source Data Verification
SFQ	Site Feasibility Questionnaires
SITU	Surgical Intervention Trials Unit
SMD	Standardised Mean Difference
SOC	System Organ Class
SOP	Standard Operating Procedure
TIDieR	Template for Intervention Description and Replication
TMF	Trial Master File
TMG	Trial Management Group
TNF	Tumour Necrosis Factor
TSC	Trial Steering Committee
UEG	United European Gastroenterology
UK NICE	United Kingdom National Institute for Health and Care Excellence

8 BACKGROUND INFORMATION AND RATIONALE

Oesophageal and gastric cancer current surveillance strategy evidence

There are over 15,800 new cases of oesophageal or gastric cancer diagnosed per year in the UK, with over 12,300 deaths attributed to these cancers annually [1,2]. The mainstay of curative treatment for oesophageal and gastric cancer is surgical resection, either with or without oncological adjunctive therapy. Despite some improvements in the survival for patients with oesophageal or gastric cancer, attributed to the improved early detection and greater utilisation of multimodal treatment [3-5], approximately 60% of patients with locally advanced and localised disease treated with curative intent will develop tumour recurrence and die within 3 years of completing treatment [4,6–8].

In the absence of robust scientific evidence, it is unsurprising that national or international guidelines fail to reach consensus on a common surveillance strategy after the treatment of oesophageal or gastric cancer. The National Comprehensive Cancer Network (NCCN) advocates regular cross-sectional imaging with computerised tomography (CT) for patients with locally advanced disease (cT2-4 N any) [9]. In contrast, the European Society for Medical Oncology (ESMO) guidelines state that neither routine imaging nor endoscopic surveillance is advocated [10]. The United Kingdom National Institute for Health and Care Excellence (UK NICE) guidelines based upon a lack of evidence currently state, 'for people without symptoms or evidence of residual disease after treatment for oesophago-gastric cancer with curative intent, do not offer routine clinical follow-up or radiological surveillance solely for the detection of recurrent disease' [11].

There has yet to be a randomised controlled trial (RCT) that has compared survival between oesophago-gastric cancer patients undergoing different surveillance protocols. This RCT is timely as there is considerable interest in the oesophago-gastric cancer community in pursuing this. NICE have highlighted that follow-up is one of the key areas for research in upper gastrointestinal cancer and have posed the key research question, 'is routine use of CT and tumour markers effective in detecting recurrent disease suitable for radical treatment in asymptomatic people who have had treatment for oesophago-gastric cancer with curative intent?' [11]. In order to answer this question, a national RCT is required.

UK current surveillance strategy

The UK NICE guidelines state, 'for people without symptoms or evidence of residual disease after treatment for oesophago-gastric cancer with curative intent, do not offer routine clinical follow-up or radiological surveillance solely for the detection of recurrent disease'[11]. A questionnaire study that we undertook of 27 oesophago-gastric UK specialist centres published online in August 2021 found that 43% of centres did not have a specific routine post-operative surveillance protocol [12]. Moreover, only 16% of centres provide routine radiological follow-up while 13% provide routine endoscopic follow-up. Upon further questioning, the most significant factor determining the intensity of surveillance was clinical presentation (82%), followed by pathologic staging (43%), margin status (36%), weight trajectory (36%) and patient preference (36%). Furthermore, there were widely different beliefs around the prognostic influence of intensive surveillance, with 31% in agreement that intensive surveillance may improve overall survival through the earlier detection of local recurrence, while 34% were not in favour of intensive surveillance, and 49% felt intensive surveillance may increase patient's anxiety. Given the significant variation in opinion, there was a

near unanimous willingness (94% agreement) to participate in an RCT to empirically evaluate the prognostic value of intensive surveillance after oesophageal and gastric cancer resections [12].

Why is this research important in terms of improving the health and/or wellbeing of the public and/or to patients and health and care services?

As stated by the current UK NICE guidance, the potential benefits to patients and the NHS of this research are clear: 'Detection of early recurrence potentially suitable for radical treatment offers the possibility of increased survival. However, the best methods of detecting recurrence are unclear and there is currently no evidence to determine whether early detection leads to improved overall survival. Studies examining the role of screening in this scenario would show whether routine surveillance in asymptomatic people was effective at detecting recurrence and improving overall survival' [11]. A large majority of patients who undergo curatively intended treatment (including extensive surgery) for oesophageal or gastric cancer die from tumour recurrence within 3 years of treatment, often due to late presentation with widely disseminated recurrence.

In addition to assessing mortality and recurrence, it is vital to also capture the impact of surveillance strategies upon wellbeing after curatively intended treatment. Previous investigations have suggested that routine clinical and radiological surveillance does reduce patients fear around cancer recurrence and provide them with reassurance, improving their overall Health-Related Quality of Life (HRQoL) [13]. Thus, following close consultation with charities and patient groups, we have ensured that this research will evaluate not only the potential prognostic benefits of a structured follow-up regime, but also the potential impacts upon patient anxiety and quality of life.

The cost-benefit of an intensive surveillance programme after oesophageal and gastric cancer treatment has not been previously studied. Thus, we have endeavoured to incorporate a robust cost-effectiveness analysis to better understand the financial costs associated with the two strategies that will be compared.

Systematic review of surveillance studies

We have completed a systematic review and meta-analysis to assess the available evidence investigating the usefulness of surveillance protocols in patients who had undergone oesophageal or gastric cancer surgery [14]. There were no RCTs, however, 15 cohort studies that described a surveillance protocol for post-operative patients with a surveillance period of at least 12 months were included. We noted that there was a large degree of heterogeneity in the structure of surveillance protocols between studies. Random-effects analysis demonstrated a statistically significant higher detection of recurrence (Overall Response (OR) 2.76, 95% Confidence Interval (CI) 1.78-3.97, P=0.01) and post-recurrence survival (Standardised Mean Difference (SMD) 14.15, 95% CI 1.40-27.26, P=0.03) with imaging-based planned surveillance post-oesophagectomy. However, the detection of recurrence (OR 0.73, 95% CI 0.11-5.12, p=0.76) and post-recurrence survival (SMD 6.42, 95% CI -2.16-18.42, P=0.14) were not significantly different with planned surveillance for gastric cancer. We concluded that an RCT is required to; (1) evaluate the potential survival benefits of intensive surveillance strategies, (2) to determine the optimal surveillance protocol and (3) to appropriately tailor it towards the target population [14].

European Investigation of Surveillance after Resection for Esophageal cancer (ENSURE study)

We undertook a European multi-centre cohort study (ENSURE). In phase 1 of this study, we surveyed 27 high-volume European centres and identified there was a large degree of heterogeneity in how centres undertook surveillance, with 37% performing intensive surveillance with annual computerised tomography (CT) or Positron Emission Tomography-CT (PET-CT). This survey also established a wide range of beliefs regarding the merits or not of an intensive surveillance strategy. Importantly, however, a high level of agreement (92%) was reached regarding the need for an RCT to study this issue.

In phase 2, 4972 patients were recruited from 20 centres, of which 47% were subject to an intensive surveillance strategy with CT or PET-CT every 6 to 12 months for the first five years after treatment. Intensive surveillance was independently associated with an increased detection of isolated local or anastomotic recurrence, and an improved overall survival (P=0.012) [15].

The results from ENSURE are important in the development and providing the rationale for this present RCT because:

(i) The survey established that there is widespread heterogeneity in surveillance protocols in Europe, and the vast majority of centres agreed there is a need for an RCT examining this issue. (ii) Intensive surveillance was associated with increased detection of isolated or anastomotic recurrence and improved overall survival.

Barriers to intensive surveillance after curatively intended treatment

The ENSURE study identified three key barriers to intensive surveillance strategies after curatively intended treatment of oesophageal or gastric cancer [15]:

(i) Uncertainty whether additional surgical or oncological treatment of recurrence improves survival

Historically, there has been an impression that the detection of recurrence or metastases in oesophageal or gastric cancer treatment will have little role in improving survival. However, we performed a systematic review and meta-analysis for the management of gastric cancer patients with liver metastases which showed that surgical resection of metastases improved overall survival (P<0.001) [16]. We have also undertaken a systematic review of oligometastatic disease in oesophageal cancer which has demonstrated improved overall survival if treated actively [17]. Furthermore, the ENSURE study suggests that intensive surveillance is associated with an increased detection of isolated local or anastomotic recurrence and that surgical treatment, with or without chemoradiotherapy, improved overall survival [15].

(ii) High costs of intensive surveillance

Regular radiological and endoscopic centred surveillance is costly. In the absence of an empirically proven survival benefit, the financial cost may be deemed to be prohibitive to establishing a nationally mandated surveillance programme. As such, undertaking a cost-effectiveness analysis of a structured surveillance pathway compared to standard care will be a key outcome measure for this RCT.

(iii) Potential impact upon Health-Related Quality of Life (HRQoL) and specifically anxiety from intensive surveillance

The ENSURE study, which is described above, consisted of 4972 patients from 20 centres and included an analysis of HRQoL. On multivariable analysis, intensive surveillance was not associated

with global health status (P=0.160), emotional functioning (P=0.209) or financial difficulties (P=0.627). However, patients undergoing intensive surveillance did exhibit greater anxiety scores (P=0.016) but also reduced dysphagia scores (P=0.006) [15]. As part of the patient involvement prior to this clinical study, we also conducted a survey study of 107 former oesophageal or gastric cancer patients, to specifically ask about potential increases in anxiety associated with intensive surveillance. We found that only 17% of respondents felt that intensive surveillance may be likely to increase their anxiety. Furthermore 78% of patients felt that intensive surveillance would be reassuring for them regarding their ongoing cancer care and monitoring for recurrence. Given these disparate findings, we believe that an analysis of HRQoL, including anxiety, will be a key secondary outcome measure within this RCT.

Definition of alarm symptoms for standard care

We have undertaken a Delphi consensus process from 24 high-volume international oesophagogastric cancer centres to define the critical symptomatic threshold that should stimulate further endoscopic or radiological investigation for cancer recurrence. The symptoms that reached at least 80% consensus for investigation were; dysphagia to solid food, dysphagia to liquids, vomiting, abdominal pain, chest pain, regurgitation of foods, unexpected weight loss and progressive hoarseness of voice [20]. Investigations triggered by the presence of these symptoms, along-with deviations from this assigned pathway, will be recorded locally and entered onto the case report form (CRF) every 6 months during the surveillance period. Significant deviations from the established symptomatic threshold, defined as more than 10% of patients in the control arm in a 6-month period, will trigger feedback and monitoring of the participating centre.

Use of imaging techniques for active surveillance

CT scans of the chest, abdomen and pelvis will be performed at 6 monthly intervals for 3 years post-randomisation.

Timing of intervention follow-up

The timing of intensive surveillance was based upon two previous studies:

1. The ENSURE cohort study suggested a timing of the intensive surveillance with CT (every 6-12 months) and an endoscopy at 12 months was prognostically important.

2. In systematic review of surveillance studies, 11 out of 15 studies utilised an intensive surveillance protocol with a CT or PET-CT at least every 6-12 months for the first two to three years after surgery

The final decision for the intervention follow-up was made to include clinical follow-up and CT every 6 months for 3 years and an endoscopy at 12 months post-randomisation.

9 OBJECTIVES AND OUTCOME MEASURES

9.1 Aim

The aim of the SARONG study is to determine whether intensive surveillance after completing curatively intended treatment improves survival and HRQoL in patients with oesophageal or gastric cancer.

9.2 Primary objective and outcome measure

Objective	Outcome measure	Time point(s) of evaluation of this outcome measure (if applicable)	Data required	Source data (including location)
To assess whether intensive surveillance, including radiological investigations and an endoscopic investigation after completing curatively intended treatment, improves survival in patients with oesophageal or gastric cancer.	All-cause mortality defined as death from any cause. Participants who have not been observed to die during the course of the study will have their survival time censored at their last known follow-up date.	3 years post- randomisation of the last included participant.	Date of randomisation. Date of death. Date last known alive if not dead.	Participant's medical notes.

9.3 Secondary objectives and outcome measures

Objectives	Outcome measures	Time point(s) of evaluation of this outcome measure (if applicable)	Data required	Source data (including location)
 To determine the impact of intensive surveillance upon the detection and treatment of 	a) Disease-specific mortality, defined as known oesophageal or gastric cancer recurrence at the time of death.	3 years post- randomisation of the last included participant.	Cause of death Date of death Last date known alive and oesophageal or gastric cancer recurrence free.	Participant's medical notes.
cancer recurrence.	 b) Pattern of tumour recurrence, defined as the incidence of loco- regional or distant recurrence. c) Treatment of 	3 years post- randomisation of the last included participant. 3 years post-	Site of recurrence as defined as loco- regional, distant or mixed. Treatment of	Participant's medical notes including CT reports. Participant's medical
	tumour recurrence,	randomisation of	recurrence as	notes.

		ie. the requirement for chemotherapy, surgery, immunotherapy, radiotherapy, chemoradiotherapy, best supportive care or other as determined by the clinical team at the treating site.	the last included participant.	allocated, along- with compliance to and completion of treatment.	
		d) Rates of oligometastatic (one site) tumour recurrence.	3 years post- randomisation of the last included participant.	Site of recurrence as defined as oligometastatic.	Participant's medical notes including CT reports.
		e) Rates of multi- metastatic (several sites) tumour recurrence.	3 years post- randomisation of the last included participant.	Site of recurrence as defined as multi- metastatic.	Participant's medical notes including CT reports.
2.	To determine the impact of surveillance upon health- related quality of life.	HRQoL, including anxiety or depression and worry of cancer returning as measured by the following validated questionnaires: EQ- 5D-5L, EORTC QLQ- C30 and QLQ-OG25 and Cancer Worry Scale (CWS).	At baseline, 6, 12, 18, 24, 30 and 36 months post- randomisation.	EQ-5D-5L EORTC QLQ-C30 EORTC QLQ- OG25 CWS.	Participant-reported outcome (questionnaires administered and data collected centrally).
3.	To assess the cost- effectiveness of routine clinical, radiological investigations and an endoscopic investigation compared with the current practice, led by clinical symptomatic follow-up.	Incremental cost per quality adjusted life year (QALY).	Healthcare Resource usage data to be collected at baseline 6, 12, 18, 24, 30 and 36 months post- randomisation.	EQ-5D-5L Healthcare Resource use questionnaires Date of death.	Participant-reported outcome (questionnaires administered and data collected centrally) Participant's medical records for resources used in secondary care.

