10.6 Use of NHS England data (including data from registries)

The NOGCA is commissioned by the Healthcare Quality Improvement Partnership (HQIP) as part of the National Clinical Audit and Patient Outcomes Programme (NCAPOP). The data processes and validation of the entered data has been well established for patients receiving surgery for oesophageal and gastric cancer since 2012. This national audit is used by all oesophago-gastric specialist cancer centres in England and Wales for the entry of oesophageal and gastric cancer patients undergoing treatment both curative and palliative.

Participants from the SARONG study will be consented for linkage of their data to the Office of National Statistics (ONS) and NOGCA datasets. Locally collected data from participant medical records will be checked against mortality data from ONS, and from NOGCA.

Patients that decline to take part in the study will continue to have their data collected as part of their normal clinical surveillance and recorded within NOGCA. Data will also be collected regarding

additional radiological and endoscopic imaging during surveillance, to evaluate if a change in surveillance protocols has been observed within participating centres during the study, in non-study participants. Thus, the external validity of the study findings will be tested through comparison of the SARONG study data, with NOGCA data from non-participating patients and centres.

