14.2 Usual care (comparator/control)

Participants randomised to the comparator arm will receive standard care follow-up following their surgery. Standard care comprises of a clinical review at 6 and 12 months and after 12 months, participants are either discharged to primary care or clinically reviewed annually by the treating centre, with targeted investigations as needed. Targeted investigations are recommended in the event of new onset alarm symptoms (see section 14.2.1 below).

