17.2.2 Follow-up assessments/subsequent visits

6, 12, 18, 24, 30 and 36 months post-randomisation

So	urced/collected by local study team	Direct patient report
Со	mpleted at hospital by local study team	
me	mber from medical notes or with participant	
٠	Blood test results	 Health-related quality of life questionnaires
•	CT-scan results (intervention arm only)	 EQ-5D-5L (unmodified)
٠	Further radiological or endoscopic	○ EORTC QLQ-C30
	investigations	○ EORTC QLQ-OG25
•	Reason for further investigation (both	○ CWS
	arms)	 Healthcare Resource use questionnaire
•	Locoregional or distant tumour recurrence	
٠	Date of mortality and cause of mortality	
•	Treatment of tumour recurrence	
•	Endoscopy results (Intervention arm only) #	
•	Resource use in secondary care	
# c	ollected at 12 month time-point only	

Questionnaire administration

Questionnaires will be sent at the time points specified above and according to the schedule set out in the Data Management Plan, and with 2 follow up reminders. For participants who have failed to return questionnaires, the central research team will check their clinical status with the local study team and then attempt to obtain the data over the telephone using the relevant script for that questionnaire, detailed below. Participants with limited English who are unable to complete these

over the telephone may be offered additional electronic or postal forms, to complete at home to allow them to access their support networks directly.

EQ-5D-5L: The self-complete version for use in REDCap will be used for participants completing the questionnaire electronically. The self-complete version on paper may also be used. Where participants have failed to return questionnaires, the central research team will check their clinical status with the local study team and then attempt to obtain the data over the telephone using the EQ-5D-5L telephone interviews scripts.

Where necessary, permission for use of all validated questionnaires used in this study have been obtained.

Self-reported Healthcare Resource Use Questionnaire: The Healthcare Resource Use Questionnaire in REDCap will be used for participants completing the questionnaire electronically. The Healthcare Resource Use Questionnaire on paper may also be used. Where participants have failed to return questionnaires, the central research team will check their clinical status with the local study team and then attempt to obtain the data over the telephone.

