17.2.4 CT scans (intervention/active surveillance arm only)

Participants randomised to the intervention arm (intensive surveillance) will have a chest, abdomen and pelvis CT scan performed every 6 months for 36 months post-randomisation.

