17.2.5 Further endoscopic/radiological investigation – both arms

Participants randomised to either arm will undergo further endoscopic or radiological investigation for cancer recurrence if they report any of the following symptoms during clinical review either within the study or outside of the study as part of normal clinical practice:

- dysphagia to solid food
- dysphagia to liquids
- vomiting
- abdominal pain
- chest pain
- regurgitation of foods
- unexpected weight loss
- progressive hoarseness of voice.

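### Disease-specific mortality counts only deaths with recurrence already known, and the scheduled scans that make recurrence known are given to the surveillance arm alone

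*Protocol*

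**What the plan says.** Section 9.3, item 1a, gives the outcome as "Disease-specific mortality, defined as known oesophageal or gastric cancer recurrence at the time of death". The same row asks for cause of death, date of death and "Last date known alive and oesophageal or gastric cancer recurrence free". Cause of death is therefore collected, and section 17.2.2 repeats it as "Date of mortality and cause of mortality", but the definition does not use it.

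The arms differ in how recurrence is sought:

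- **Surveillance** (17.2.3, 17.2.4): an endoscopy at 12 months and a "chest, abdomen and pelvis CT scan performed every 6 months for 36 months post-randomisation".
- **Control** (14.2): clinical review at 6 and 12 months, after which "participants are either discharged to primary care or clinically reviewed annually by the treating centre, with targeted investigations as needed".
- **Both arms** (17.2.5): "Participants randomised to either arm will undergo further endoscopic or radiological investigation for cancer recurrence if they report any of the following symptoms". For control, section 14.2.1 leaves this to the local centre's discretion.

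The trial is open label (section 10). Local teams record disease-specific mortality from the medical record, and registry validation is described for all-cause mortality (10.2, 10.3). Section 20.4 analyses disease-specific survival with the time-to-event methods used for the primary outcome.

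**The concern.** The outcome has detection built into it, and detection is what the intervention changes. Two errors follow, and they act in the same direction.

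1. A control participant who dies of recurrence that nobody diagnosed is not an event.
2. A surveillance participant who dies of something else, with recurrence already seen on a scheduled scan, is an event.

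The objective above this outcome concerns the effect of surveillance on detecting and treating recurrence, so a difference in detection is expected by design. No blinded review of cause and no equal check for recurrence at or after death is described. The central re-read of CT images (10.5.1) covers only scans that were taken.

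At stake is one secondary between-arm comparison. It could show an excess of disease-specific deaths under surveillance where none exists, or hide part of a real benefit. A reader would also find it hard to reconcile with the all-cause result.

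**Working it through.** **The plan's own figures (section 20.2).** HR = ln(0.55)/ln(0.45) = 0.749, as stated. Events for 90% power at two-sided 5% are 4 × (1.960 + 1.282)² / (ln 0.749)² ≈ 502, which equals the stated 273 + 229. The primary design is not in question. The protocol states no figure for disease-specific mortality.

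**Inputs that the protocol does not give (assumptions).**
- Share of cancer deaths with recurrence known before death: 98–99% under surveillance (s), 80–95% in control (c).
- Share of all deaths that are cancer deaths (f): 80–90%.
- Shares s and c are constant over time. The second error (other-cause deaths with scan-detected recurrence) is left out, and would add to the figures below.

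**Step 1: spurious hazard ratio with no true effect.** If the cancer-death hazard is equal in both arms, the recorded hazard in each arm is that hazard times the share known, so the apparent HR is s/c.

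| Known in control (c) | s = 98% | s = 99% |
|---|---|---|
| 95% | 0.98/0.95 = 1.03 | 0.99/0.95 = 1.04 |
| 90% | 0.98/0.90 = 1.09 | 0.99/0.90 = 1.10 |
| 85% | 0.98/0.85 = 1.15 | 0.99/0.85 = 1.16 |
| 80% | 0.98/0.80 = 1.23 | 0.99/0.80 = 1.24 |

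**Step 2: chance of a significant result against surveillance when there is no effect.** Take 502/2 = 251 deaths per arm. Recorded events are D = 251 × f × (s + c), and the chance is Φ[(√D/2) × ln(s/c) − 1.96]; the nominal value is 2.5%.
- Mild end (f = 0.8, s = 0.98, c = 0.95): D = 196.8 + 190.8 = 387.6; (√387.6/2) × ln 1.032 = 0.31; chance about 5%.
- Severe end (f = 0.9, s = 0.99, c = 0.80): D = 223.6 + 180.7 = 404.3; (√404.3/2) × ln 1.2375 = 2.14; chance about 57%.

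**Step 3: if the design effect is real and applies equally to cancer deaths.** The apparent HR is 0.749 × s/c, which runs from 0.749 × 1.032 = 0.77 to 0.749 × 1.2375 = 0.93. With every cancer death counted, power on this outcome would be about 83% (f = 0.8) to 87% (f = 0.9), from Φ[(√(502f)/2) × |ln 0.749| − 1.96]. With the misclassification, using D = f × (229s + 273c) and the apparent HR, it runs from about 77% (f = 0.9, s = 0.98, c = 0.95) down to about 11% (f = 0.8, s = 0.99, c = 0.80).

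The direction is the same in every cell because s exceeds c throughout. The size rests entirely on the assumed gap.

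**The case against.** The best defence is that the gap in detection by the time of death may be small. Recurrence that kills usually causes symptoms. Section 17.2.5 sends participants in either arm for investigation on any of eight symptoms, and the footnote to the 17.1 schedule says control participants are evaluated for trigger symptoms. Outcome data are collected in both arms every six months. The background (section 8) describes recurrence that presents late and widespread, which means found late rather than never found. The source for this outcome is the medical notes, so a clinical diagnosis could make recurrence known without a scheduled scan. Scheduled scanning also stops at 36 months, while deaths are collected until 36 months after the last randomisation (10.3), which dilutes any effect. All of this stands, and it points to the low end of the range.

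A reader might take the protocol's own meta-analysis, where "Random-effects analysis demonstrated a statistically significant higher detection of recurrence" (OR 2.76 after oesophagectomy), as a measure of the bias. It is not. It comes from cohort studies and concerns detection of recurrence overall, not recurrence known among those who died. The gastric estimate in the same paragraph is OR 0.73 (95% CI 0.11–5.12), so the supporting evidence is oesophageal only, and the trial enrols both cancers.

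The second error is probably minor. With about 60% said to develop recurrence and die within three years (section 8), against 55% control all-cause mortality (20.2), other-cause deaths should be few.

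It can also be said that the SAP may combine known recurrence with recorded cause. It may, but the protocol already fixes a definition, and that definition does not use cause.

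**Conclusion.** The point holds as a bias of known direction and unknown size in one secondary outcome. Under the stated definition, the disease-specific comparison is tilted against surveillance whenever recurrence is more often known before death in that arm. On the assumed shares the spurious hazard ratio is about 1.03 to 1.24; the lower values are plausible and the higher ones need 15–20% of control cancer deaths to have unrecognised recurrence, which nothing in the protocol shows.

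A reader might infer that the trial will report excess disease-specific deaths under surveillance. The protocol does not support that: it gives no share of deaths with recurrence known in either arm, and a true benefit could outweigh the bias. Nor does the point reach the primary outcome, since all-cause mortality does not depend on knowing about recurrence. The wording should be changed, but the main conclusion of the trial does not hang on it.

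**What to change.** In section 9.3 (1a), and correspondingly in the SAP, define disease-specific death as death with oesophageal or gastric cancer as the underlying cause, by the same rule in both arms and whether or not recurrence was diagnosed before death. Use the cause of death already collected on the CRF, and the ONS cause where the linkage extract includes it. Section 10.6 provides for consented ONS linkage but describes its use for checking mortality data, so the sponsor should confirm that cause is in the extract. Review of cause blinded to allocation would strengthen the rule, since local teams know the arm. Keep recurrence known at death as a sensitivity analysis or descriptive item.

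The cost is mainly wording, with no new visits and no new CRF item; obtaining the ONS cause, if it is not already in the extract, or adding blinded review would cost more. The downside is that recorded cause carries some misclassification and is not fully independent of scan results, because a certifier may know them. But detection would no longer be a condition for counting the death. The change is best made before anyone sees outcome data by arm.
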